Figure 2 provides a study schematic indicating visit structure for each individual cohort. After initial Screening, eligible patients will return to the study site at weekly intervals throughout the Treatment Period for study drug administration and safety, PK, PD, efficacy, and other assessments. Enrolled patients will also return to the study site between study drug administration visits for the assessment of PK/PD endpoints. Primary and secondary efficacy endpoints will be assessed at the End-of-Treatment Visit on Day 43. During the 4-week Follow-up Period, patients will return to the study site at 2 weeks and 4 weeks after the end of the Treatment Period for additional assessments.

Santarus, Inc.
SAN-300
Confidential
Clinical Trial Protocol: C2013-0302

Amendment 5: 28 Mar 2016

Figure 1. Study Design for Study C2013-0302

Abbreviation: PBO = placebo; QW = every week; QOW = every other week.

Notes: Patients will be randomized to each cohort in a 3:1 ratio of SAN-300 to placebo. A Safety Committee Review will occur after patients have completed the 6-week Treatment Period of each cohort. Any subject who withdraws prior to the end of the 6-week Treatment Period will not be replaced and the Study Safety Committee will review the data from all subjects regardless of duration of participation in the study.

Randomization Primary Efficacy Endpoint Last Visit Screening Treatment Period Follow-up Period SAN-300 SC (N=30) Screening Period Placebo SC (N=10) Visit: 1 2 3 4 5 6 7 8 9 10 Dav: -21 1 8 15 22 29 36 43 57 71 Week: 1 7 11

Last weekly SAN-300 dose

Last every-other-week SAN-300 dose

Figure 2. Study Design for Individual Cohorts

Abbreviation: SC = subcutaneously.

Screening: Between Days -21 and -1. Informed consent will be obtained before any study specific procedures are performed. Eligibility assessments will be performed.

Treatment Period: Days 1 to 43. Baseline assessments and measurements will be performed before dosing with study drug. Patients will receive SC injections of study drug as follows:

- For all cohorts, patients randomized to receive placebo will be administered a total of six once-weekly injections of placebo on Days 1, 8, 15, 22, 29, and 36.
- In Cohorts A, B, E and F, patients randomized to receive SAN-300 will be administered a total of six weekly injections of SAN-300 on Days 1, 8, 15, 22, 29, and 36.

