- In Cohorts C and D, patients randomized to receive SAN-300 will be administered a total of three every-other-week injections of SAN-300 on Days 1, 15, and 29 and will be administered a total of three every-other-week injections of placebo on Days 8, 22, and 36.

Study assessments and measurements will be performed on Days 1, 8, 15, 22, 29, 36, and 43. Patients will also visit the clinic between study drug administration visits for the assessment of PK/PD endpoints. The primary and secondary efficacy endpoints will be assessed at the End-of-Treatment Visit on Day 43.

Follow-up Period: Days 43 to 71. Study patients will return for follow-up visits on Days 57 and 71 for safety and efficacy assessments. The Exit Visit will occur on Day 71. Patients who withdraw early from the study must return to the clinic to complete the Exit Visit assessments.

Study procedures at each visit are described in the Schedule of Assessments, provided as Appendix 2.

Amendment 5: 28 Mar 2016

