3.2 Rationale for Study Design and Control Group

3.2.1 Rationale for Dosing Regimen

The planned doses (0.5 mg/kg once weekly through 4.0 mg/kg every week) and duration of study treatment are based on the observed safety, PK, and PD profile of SAN-300 (including VLA-1 receptor occupancy) in Phase 1 single-dose Study 301 and data from up to 3 months of dosing in non-human primate studies (Section 1.2.3). Based on receptor occupancy data, SAN-300 2.0 mg/kg SC resulted in durable VLA-1 receptor occupancy through Day 8 and the 4.0 mg/kg SC dose extended this receptor occupancy through approximately Day 15. These results suggest that weekly or every-other-week dosing may be sufficient to maintain a therapeutic effect.

In Study 301, single doses of SAN-300 up to 6.0 mg/kg SC were tolerated in a healthy volunteer population. To ensure patient safety, the design of the current multiple ascending dose study stipulates a Safety Review to occur after each dosing Cohort. The overall drug exposure in each cohort is as follows:

Table 1 Overall Study Drug Exposure by Cohort

Cohort	SAN-300 Dose Regimen	Overall Exposure
A	0.5 mg/kg QW	3.0 mg/kg
В	1.0 mg/kg QW	6.0 mg/kg
С	2.0 mg/kg QOW	6.0 mg/kg
D	4.0 mg/kg QOW	12.0 mg/kg
E	4.0 mg/kg QW	24.0 mg/kg
F	2.0 mg/kg QW	12.0 mg/kg

Abbreviations: QOW = every other week; QW = every week

Both weekly and every-other-week dosing will be explored to investigate appropriate dosing parameters for SAN-300. Should every-other-week dosing be a viable option for treatment of patients with RA, this dosing regimen would decrease patient burden.

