3.2.2 Rationale for Control Group

In every cohort, 6 patients will be randomized to receive SAN-300 and 2 patients will be randomized to receive placebo. Placebo injections will be the best control for potential injection-site AEs, which were observed in the Phase 1 Study 301. Regardless of the cohort, all patients randomized to receive placebo will be administered a total of six once-weekly injections of placebo. In Cohorts C and D, patients randomized to receive SAN-300 will be administered three every-other-week injections of SAN-300 and three every-other-week injections of placebo on alternating weeks. In this way, cohorts with patients receiving every-other-week study drug injections will have matched placebo controls while, at the same time, patients on placebo from all six cohorts (totaling N = 10) can be pooled for safety and efficacy analyses.

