Appendix 2 Schedule of Assessments for Study C2013-0302

	Screening (21 days)			Dou	ble-blind T	reatment Po	ent Period (42 days [3 to 6 doses])					Follow-up Period (28 days)		
Week:		Wee	k 1	Week 2	Week 3	Week 4	We	ek 5	We	ek 6	Week 7	Week 9	Week 11	
Visit:	Visit 1	Visit 2 Day 1 ^a		Visit 3	Visit 4	Visit 5	Visit 6 Day 29 ^a		Visit 7 Day 36 ^a		Visit 8	Visit 9	Visit 10	
Day:	Day -21 to -1			Day 8 ^a	Day 15 ^a	Day 22 ^a					Day 43 ^a	Day 57 ^a	Day 71 ^a	
Timing (where applicable):		Pre-dose	Post- dose				Pre- dose	Post-dose	Pre- dose	Post- dose	End-of- Treatment Visit		Exit Visit	
Eligibility Assessments		 		t		'		 		L	.		 	
Informed Consent	X													
Inclusions/Exclusions	X	Х												
Demographics	X													
Medical History	X	Х												
Medication History	X	Х												
RA History and Prior RA Treatment	Х	Х												
HCV Antibody, HBsAg, HIV Antibody	Х													
Chest X-ray ^b	Х													
QuantiFERON-GOLD	X													
Dosing		 		1		'							 	
Randomization		Х												
Administration of SAN-300 or Placebo ^c		Xď		Xc	Х	Xc	Х		Xc					
Safety Assessments														
Vital Sign Measurements	Х	Х	X^g	X ^g	X ^g	X ^g	Χ	X ^g	Χ	X ^g	Х	Х	Х	
Physical Examination	Х										Х		Х	
CBC, Chemistry Panel	Х	Х		Х	Х	Х	Х		Х		Х	Х	Х	
UA	X	Х									X		Х	
INR, PT, aPTT, Complement		Х									Х		Х	

Santarus, Inc.

SAN-300

Amendment 5: 28 Mar 2016

CONFIDENTIAL Clinical Trial Protocol: C2013-0302

Page 64 of 118

	Double-blind Treatment Period (42 days [3 to 6 doses])										Follow-up Period (28 days)		
Week:		Week 1 Visit 2 Day 1 ^a		Week 2	Week 3	Week 4	Week 5 Visit 6 Day 29 ^a		Week 6 Visit 7 Day 36 ^a		Week 7 Visit 8 Day 43 ^a	Week 9	Week 11
Visit:	Visit 1			Visit 3	Visit 4	Visit 5						Visit 9	Visit 10
Day:	Day -21 to -1			Day 8 ^a	Day 15 ^a	Day 22 ^a						Day 57 ^a	Day 71 ^a
Timing (where applicable):		Pre-dose	Post- dose				Pre- dose	Post-dose	Pre- dose	Post- dose	End-of- Treatment Visit		Exit Visit
Tryptase, histamine ^e		Х											
Serum Immunoglobulins		Х									Х		Х
12-Lead ECG	X										Х		
Pregnancy Test	Serum	Urine				Urine			Urine		Serum		
Adverse Events	Х	Х	Х	Х	Х	Х	Х	Х	Х	Х	Х	Х	Х
Concomitant Medications		Х	Х	Х	Х	Х	Х	Х	Х	Х	Х	Х	Х
Efficacy Assessments													
ACR Core Set Assessments, DAS28-CRP	Х	Х		Х	Х	Х	Х		Х		х	Х	Х
HAQ-DI	Х	Х		Х	Х	Х	Х		Х		Х	Х	Х
ESR	Х	Х		Х	Х	Х	Х		Х		Х	Х	Х
CRP	Х	Х		Х	Х	Х	Х		Х		Х	Х	Х
MRI of Hand and Wrist ^f		Х									Х		

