Other Assessments		.		L	L	 		 		L	· L		.4
RF, ACPA	Х										Х		
ANA		Х									Х		

Abbreviations: ACPA = anti-citrunillated peptide antibodies; ACR = American College of Rheumatology; ANA = antinuclear antibody; aPTT = activated partial thromboplastin time; CBC = complete blood count with differential and platelet count; CCP = cyclic citrullinated peptide; DAS28-CRP = Disease Activity Score with 28-joint count C-reactive protein; ECG = electrocardiogram; ESR = erythrocyte sedimentation rate; HAQ-DI = Health Assessment Questionnaire – Disease Index; HBsAg = hepatitis B surface antigen; HCV = hepatitis C virus; HIV = human immunodeficiency virus; CRP = C reactive protein; INR = international normalized ratio; MRI = magnetic resonance imaging; PT = prothrombin time; QFT = QuantiFERON®-TB Gold test; RA = rheumatoid arthritis; RF = rheumatoid factor; UA = urinalysis.

Weekly visits during the Treatment and Follow-up Periods can be scheduled for ±2 days around each of the designated Days in this schedule, but the designated Days themselves will not be shifted relative to Day 1.

b If a chest X-ray was performed with no clinically significant findings within 1 month of randomization, another chest X-ray is not required at Screening.

Santarus, Inc. SAN-300

Amendment 5: 28 Mar 2016

CONFIDENTIAL Clinical Trial Protocol: C2013-0302

Page 65 of 118

For all cohorts, patients randomized to receive placebo will be administered a total of 6 once-weekly SC injections of placebo on Days 1, 8, 15, 22, 29, and 36. In Cohorts A, B, and D, patients randomized to receive SAN-300 will be administered a total of 6 once-weekly SC injections of SAN-300 on Days 1, 8, 15, 22, 29, and 36. In Cohorts C and E, patients randomized to receive SAN-300 will be administered a total of three every-other-week SC injections of SAN-300 on Days 1, 15, and 29 and will be administered a total of three every-other-week SC injections of placebo on Days 8, 22, and 36. Note: Subject to be observed at minimum 1 hour post- dose. Longer observation allowed if deemed necessary by investigator or designee.

- d Day 1 dosing will occur on the day of or within 24 hours after randomization.
- ^e After baseline assessment, additional assessments of tryptase and histamine to occur only in suspected cases of anaphylaxis or hypersensitivity reactions.

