Notes: Patients will be randomized to each cohort in a 3:1 ratio of SAN-300 to placebo. A Safety Committee Review will occur after patients have completed the 6-week Treatment Period of

each cohort. Any subject who withdraws prior to the end of the 6-week Treatment Period will not be replaced and the Study Safety Committee will review the data from all subjects regardless of duration of participation in the study.

Figure 2 provides a study schematic indicating visit structure for each individual cohort. After initial Screening, eligible patients will return to the study site at weekly intervals throughout the Treatment Period for study drug administration and safety, PK, PD, efficacy, and other assessments. Enrolled patients will also return to the study site between study drug administration visits for the assessment of PK/PD endpoints. Primary and secondary efficacy endpoints will be assessed at the End-of-Treatment Visit on Day 43. During the 4-week Follow-up Period, patients will return to the study site at 2 weeks and 4 weeks after the end of the Treatment Period for additional assessments.

Primary Efficacy Endpoint Randomization Last Visit Screening Treatment Period Follow-up Period SAN-300 SC (N=30) Screening Period Placebo SC (N=10) Visit: 1 3 4 5 6 9 10 2 7 8 Day: -21 1 8 15 22 29 36 43 57 71 Week: 1 7 11 Last weekly SAN-300 dose Last every-other-week SAN-300 dose

Figure 2. Study Design for Individual Cohorts

Abbreviation: SC = subcutaneously.

Screening: Between Days -21 and -1. Informed consent will be obtained before any study specific procedures are performed. Eligibility assessments will be performed.

Treatment Period: Days 1 to 43. Baseline assessments and measurements will be performed before dosing with study drug. Patients will receive SC injections of study drug as follows:

• For all cohorts, patients randomized to receive placebo will be administered a total of six once-weekly injections of placebo on Days 1, 8, 15, 22, 29, and 36.

- In Cohorts A, B, E and F, patients randomized to receive SAN-300 will be administered a total of six weekly injections of SAN-300 on Days 1, 8, 15, 22, 29, and 36.
- In Cohorts C and D, patients randomized to receive SAN-300 will be administered a total of three every-other-week injections of SAN-300 on Days 1, 15, and 29 and will be administered a total of three every-other-week injections of placebo on Days 8, 22, and 36.

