Abbreviations: ACPA = anti-citrunillated peptide antibodies; ACR = American College of Rheumatology; ANA = antinuclear antibody; aPTT = activated partial thromboplastin time; CBC = complete blood count with differential and platelet count; CCP = cyclic citrullinated peptide; DAS28-CRP = Disease Activity Score with 28-joint count C-reactive protein; ECG = electrocardiogram; ESR = erythrocyte sedimentation rate; HAQ-DI = Health Assessment Questionnaire – Disease Index; HBsAg = hepatitis B surface antigen; HCV = hepatitis C virus; HIV = human immunodeficiency virus; CRP = C reactive protein; INR = international normalized ratio; MRI = magnetic resonance imaging; PT = prothrombin time; QFT = QuantiFERON®-TB Gold test; RA = rheumatoid arthritis; RF = rheumatoid factor; UA = urinalysis.

^a Weekly visits during the Treatment and Follow-up Periods can be scheduled for ±2 days around each of the designated Days in this schedule, but the designated Days themselves will not be shifted relative to Day 1.

b If a chest X-ray was performed with no clinically significant findings within 1 month of randomization, another chest X-ray is not required at Screening.

^c For all cohorts, patients randomized to receive placebo will be administered a total of 6 once-weekly SC injections of placebo on Days 1, 8, 15, 22, 29, and 36.

In Cohorts A, B, and D, patients randomized to receive SAN-300 will be administered a total of 6 once-weekly SC injections of SAN-300 on Days 1, 8, 15, 22, 29, and 36. In Cohorts C and E, patients randomized to receive SAN-300 will be administered a total of three every-other-week SC injections of SAN-300 on Days 1, 15, and 29 and will be administered a total of three every-other-week SC injections of placebo on Days 8, 22, and 36. Note: Subject to be observed at minimum 1 hour post- dose. Longer observation allowed if deemed necessary by investigator or designee.

^d Day 1 dosing will occur on the day of or within 24 hours after randomization.

e After baseline assessment, additional assessments of tryptase and histamine to occur only in suspected cases of anaphylaxis or hypersensitivity reactions.

f In patients who are able to tolerate the MRI, it should be performed within 5 days prior to or at Visit 2 (Day 1, prior to dosing). MRI of hand and wrist most clinically affected by RA will be imaged at Baseline, the same wrist will be imaged at End of Treatment.

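### The dosing footnote in Protocol Appendix 2 and SAP Appendix 1 reverses the dosing frequency of Cohorts D and E relative to the rest of both documents and gives Cohort F no SAN-300 schedule

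*Protocol*

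**What the plan says.** **The footnote.** In the schedule of assessments, the row "Administration of SAN-300 or Placebo" carries superscript c on its label and on the Day 8, 22 and 36 cells. The footnote reads: "In Cohorts A, B, and D, patients randomized to receive SAN-300 will be administered a total of 6 once-weekly SC injections of SAN-300". It then puts C and E on the every-other-week regimen, with placebo on Days 8, 22 and 36. Cohort F is covered only by the sentence on placebo patients, which applies to every cohort. SAP Appendix 1 repeats the text: "In Cohorts C and E, patients randomized to receive SAN-300 will be administered a total of three every-other-week SC injections of SAN-300".

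**The rest of the protocol.** Section 3.1 has "In Cohorts A, B, E and F, patients randomized to receive SAN-300 will be administered a total of six weekly injections" and "In Cohorts C and D, patients randomized to receive SAN-300 will be administered a total of three every-other-week injections of SAN-300". The synopsis agrees. Section 3.2.2 repeats the second statement: "In Cohorts C and D, patients randomized to receive SAN-300 will be administered three every-other-week injections of SAN-300". Table 1 in Section 3.2.1 ("Overall Study Drug Exposure by Cohort") gives D as 4.0 mg/kg every other week, total 12.0 mg/kg, and E as 4.0 mg/kg weekly, total 24.0 mg/kg. Table 2 in Section 5.1 gives the same doses and frequencies.

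**The rest of the SAP.** Section 3.1 says "In Cohorts A, B, E and F, patients randomized to receive SAN-300 will be administered a total of six weekly injections of SAN-300", with C and D every other week. The SAP therefore contradicts its own Appendix 1.

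**The concern.** The primary objective is safety and tolerability in an ascending-dose study. D and E have the same mg/kg per injection, so a reader who follows the footnote and a reader who follows Table 2 would attach opposite regimens to those two cohort labels. The footnote marks exactly the days on which the product differs.

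Dosing appears to be over: SAP version 2.0 is dated 20 March 2017, and SAP Section 3.5 reports 41 patients randomized. What remains at stake is labelling. SAP Section 4 displays SAN-300 patients by cohort, while SAP Section 7.1 names the groups by dose and frequency. Joining the two needs a cohort-to-regimen map, and the SAP contains two. A swap would also affect SAP Section 7.3, which plots ACR response by dose level and frequency and models regimen as an ordinal variable.

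**Working it through.** **1. Cumulative exposure.** Exposure = dose per injection x number of SAN-300 injections (6 if weekly, 3 if every other week). Doses are from Table 2. Injection counts come first from Protocol Section 3.1, then from footnote c.

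| Cohort | Dose (mg/kg) | Section 3.1 count: exposure | Table 1 | Footnote c count: exposure |
|---|---|---|---|---|
| A | 0.5 | 6: 3.0 | 3.0 | 6: 3.0 |
| B | 1.0 | 6: 6.0 | 6.0 | 6: 6.0 |
| C | 2.0 | 3: 6.0 | 6.0 | 3: 6.0 |
| D | 4.0 | 3: 12.0 | 12.0 | 6: 24.0 |
| E | 4.0 | 6: 24.0 | 24.0 | 3: 12.0 |
| F | 2.0 | 6: 12.0 | 12.0 | not stated |

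The Section 3.1 frequencies reproduce all six Table 1 figures. The footnote frequencies match A, B and C, swap D and E, and leave F undefined. The last column is an illustration: no passage states that combination, and the Table 2 cells that supply 4.0 mg/kg state the other frequency. Agreement with Table 1 shows that those passages are consistent with one another; it does not show which regimen was given.

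**2. Administrations in conflict.** The readings differ on Days 8, 22 and 36. With 6 SAN-300 patients per cohort, 6 x 3 = 18 administrations per cohort, and 18 x 2 = 36 across D and E. Placebo patients are unaffected. No count is claimed for F.

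**3. Would the planned exposure summary reveal a swap?** SAP Section 8.1 defines extent of exposure as last dose of study drug minus first dose plus 1. The protocol defines study drug to include placebo. For a patient who completes dosing on the nominal days:

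- weekly: 36 - 1 + 1 = 36 days
- every other week, placebo injections counted: 36 - 1 + 1 = 36 days
- every other week, SAN-300 only: 29 - 1 + 1 = 29 days

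Under the protocol's definition the summary cannot separate the readings. It could only if the SAP meant SAN-300 alone, which it does not say. Table 14.1.5 also names treatment compliance, but the SAP text does not define it, and Protocol Section 5.5 says no patient compliance measures are needed.

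**4. Enrolment figures (secondary).** Six cohorts of 6 + 2 give 36 + 12 = 48; five give 30 + 10 = 40. The protocol lists six cohorts but elsewhere says five, about 40 patients, and a pooled placebo group of 10. Section 3.2.2 attributes that 10 to all six cohorts, although 6 x 2 = 12. SAP Section 3.1 plans about 48 but keeps the five-cohort wording, and its Figure 2 keeps 30 and 10. The SAP calls F optional; the protocol lists it as planned.

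**The case against.** The conflict itself is not in dispute. The case for giving it little weight is as follows.

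- **Only Table 2 is named for dosing by cohort.** Section 5.1 assigns cohort dosing to it, while Sections 3.1 and 10 cite Appendix 2 for visit procedures. Every patient in a named cohort is injected on the same six days either way, so blinded staff do the same thing. Only the unblinded preparer's product choice differs, and Section 5.2 has that person obtain the assignment centrally. This stands as a reason to think misdosing unlikely. It is not a precedence rule, and the footnote remains attached to the dosing row.
- **The analysis text does not use the footnote.** Efficacy groups are named by dose and frequency, and safety is analysed by treatment received. True, but cohort labels must still be linked to regimens, and the SAP gives two links.
- **Other records can settle what was given.** Protocol Appendix 3 schedules serum SAN-300 samples before every dose, 1 hour after the Day 36 injection and between visits; Sections 5.8.3 and 5.9 require accountability logs checked by an unblinded monitor. This stands, and these are useful further routes to the same check.
- **Cohort F and the enrolment figures are largely explained by F being optional.** Partly accepted. With 41 randomized and 2.0 mg/kg weekly missing from SAP Section 7.1, the omission of F may concern no patients. The protocol, however, does not call F optional, and the pooled-placebo statement in Section 3.2.2 remains inconsistent.
- **The added exposure rows reconcile no text.** Correct; they are a modest extra, and the finding does not depend on them.

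**Conclusion.** The concern holds. Current Amendment 5 text and the SAP each assign opposite frequencies to D and E in different places, and the footnote gives F no SAN-300 schedule. The conflict covers 36 planned administrations in D and E. If the footnote frequencies were applied at the Table 2 dose, cumulative exposure would change twofold in each cohort. No passage shows that anyone was misdosed, and no power or alpha figure is affected.

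This should be fixed. It would be essential if the protocol were still being used for dosing; the lower rating rests on the SAP's report of completed randomization. The statement that extent in days cannot separate the readings assumes that the SAP carries over the protocol's definition of study drug and that patients complete dosing on the nominal days. The enrolment inconsistencies are secondary.

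**What to change.** 1. Reconcile footnote c in Protocol Appendix 2 and SAP Appendix 1 with the synopsis, Protocol Sections 3.1 and 3.2.2, Tables 1 and 2, and SAP Section 3.1, so that every passage gives one and the same regimen for each of Cohorts A to F. Which regimen is right is for the sponsor to establish.
2. Confirm from the IVRS/IWRS and dosing records that the regimens given to D and E match the labels used in the analysis. Planned Listing 16.2.5.1 can serve if it shows date, product (SAN-300 or placebo) and dose for each administration; the SAP does not now specify its content.
3. Add the number of SAN-300 administrations and cumulative mg/kg by group to Table 14.1.5.
4. Reconcile the cohort and patient counts in the synopsis, Protocol Sections 3.1, 3.2.2, 4.1 and 11.1 and Figure 2, and SAP Section 3.1 and Figure 2. State consistently whether Cohort F is planned or optional.

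The cost is text corrections, one records check for two cohorts, and two rows in a table already planned. No extra patients are needed, and no power or alpha figure changes.
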